9.8 Quality of life, Physical performance and Economic assessments

The Seattle Angina Questionnaire and the EQ-5D questionnaire will be used to measure quality of life. Short physical performance battery (SPPB) will be used for physical performance evaluation. In addition, costs will be collected during the course of the study, including medical and resource utilization (including medication and cardiac procedures), re-hospitalizations and emergency room visits.

9.9 Adjudication of clinical events

A committee consisting of clinicians who are blinded to treatment allocation will adjudicate primary and secondary efficacy outcomes (death, MI, stroke, revascularization). The functioning rules and the membership of the Adjudication Committee are detailed in the Adjudication Committee Charter before the start of the trial. Adjudication results will be binding for the final analysis.

10 STATISTICAL ANALYSIS PLAN

All statistical analyses will be performed by the Centro di Ricerca Clinica ed Epidemiologica of the University of Ferrara under the supervision of [name]. Analysis will be performed on an Intention to Treat (ITT) set, defined as all intentionally randomized patients, by randomization treatment. Supportive per-protocol analyses will be performed on the primary and key secondary endpoints. A detailed statistical analysis plan will be completed before the end of the study. In brief, continuous variables will be tested for normal distribution with the Kolmogorov-Smirnov test and with visual estimate of Q-Q plot. Normally distributed variables will be presented as mean±SD and compared by t test and 1-way ANOVA. Otherwise, median [inter-quartile range], Mann-Whitney U and Kruskal-Wallis tests will be used. Categorical variables will be summarized in terms of absolute and relative frequencies (percentages) and compared by using χ^2 test. One-sided tests will be done in order to check the superiority of functionally-driven complete revascularization. Statistical significance will be set at $\alpha=0.05$ level. Formal type-I error control will be ensured for the primary and the key secondary endpoint by a sequential procedure where significance for the key secondary endpoint is accepted only if the primary endpoint is positive. Kaplan-Meier curves will be plot to describe survival free from adverse events, and difference between groups will be test will log-rank test. The primary analysis will be based on events of all follow-up time of each patient at the time of the database lock. Further analyses will be performed with events after more than 30 days considered as censored, as well as after more than 365 days considered as censored. Any confounding factor will be tested by Cox regression models. Variables with a p-value <0.1 at univariate analysis will be entered into a multivariable analysis to identify the independent predictors. When appropriate, 95% CI will be calculated. In addition, we will assess the composite primary outcome POCE (all-cause mortality, any MI, any stroke and any revascularization) with the use of the Finkelstein–Schoenfeld method, which is based on the principle that each patient in the clinical trial is compared with every other patient in a pairwise manner. This method gives a higher importance to all-cause mortality. The pairwise comparison proceeds in hierarchical fashion, using all-cause mortality, followed by frequency of MI when patients cannot be differentiated on the basis of mortality and so on for the other endpoints We will apply the Finkelstein–

Schoenfeld method to the patients stratified according to clinical presentation (STE vs NSTE) and number of diseased vessels (2 vs 3), yielding four stratification pools. All analyses will be performed with STATA 13 (StataCorp, College Station, TX).

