5 STUDY OBJECTIVES

5.1 Primary objective

- To test if a functionally-driven complete revascularization is superior to a culprit only strategy in the reduction of the POCE of all-cause death, any MI, any stroke, any revascularization at 1 year in elderly patients with MI and multivessel PCI

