10.1 Determination of sample size

Data regarding death, MI, stroke and revascularization at 1 year in patients ≥ 75 years with MI and multivessel disease treated with culprit only revascularization are lacking. Taking into account available data (see tables below) and our preliminary data coming from “The frailty in elderly patients receiving cardiac interventional procedures (FRASER) program”, we estimated a conservative 15% rate of the primary endpoint at 1 year in the culprit-only strategy group. Considering that functional assessment should reduce the primary endpoint of at least 30% (see table below), 1358 patients are required to have a 80% chance of detecting, as significant at the 5% level, a 30% difference in the primary outcome between the two groups considering a 15% rate of the primary endpoint in the control group. Considering a 2% attrition rate final sample size is inflated to 1385 patients. After at least 900 patients have completed the 30-day follow-up, the assumption of the sample size calculation will be checked by estimating the Kaplan-Meier 1-year risk of having reached the primary endpoint. Unadjudicated data will be used for this purpose. No randomization information will be available and all the evaluation on the sample size will be performed in a blinded fashion. If the pooled event rate will be considerably lower than expected the sample size may be increased.

Ischemic outcome at 1 year in patients with ACS treated with culprit-only revascularization

Study	MI	Repeat revascularization	MACE
Compare acute	4.7%	17.5%	20.5%
Culprit	2.7%	8.2%	21.2%
Prami	8.6%	19.9%	22.9%
Danami-3-Primulti	5%	9%	22%
Translate-ACS	7%	17%	22%

Primary endpoint reduction with functional guided revascularization in ACS setting

Study	Primary endpoint	HR
Compare acute	MACCE*	0.35 [0.22-0.55]
Danami-3-Primulti	all-cause mortality, reinfarction, or ischaemia-driven revascularisation	0.56 [0.38-0.83]

*all-cause mortality, nonfatal myocardial infarction, any revascularization, and cerebrovascular events.

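### The objective and sample size are set at 1 year, but the primary analysis counts all events up to database lock

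*Protocol*

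**What the plan says.** All the relevant text is in the Protocol.

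- **Section 5.1 (primary objective):** superiority in "reduction of the POCE of all-cause death, any MI, any stroke, any revascularization at 1 year in elderly patients".
- **Section 10.1 (sample size):** "we estimated a conservative 15% rate of the primary endpoint at 1 year in the culprit-only strategy group". A 30% relative reduction is assumed, and "1358 patients are required to have a 80% chance of detecting, as significant at the 5% level". The blinded check of the sample size also uses a 1-year Kaplan-Meier estimate of the primary endpoint.
- **Section 10 (analysis):** "The primary analysis will be based on events of all follow-up time of each patient at the time of the database lock". Further analyses then censor events beyond 30 days, "as well as after more than 365 days considered as censored". The between-group test is the log-rank test, one-sided at 0.05. The key secondary endpoint may be claimed only if the primary is positive.
- **Section 5.2:** the same composite at 3 and 5 years is a separate secondary objective.
- **Section 8.1.7:** clinic visits continue yearly after the 1-year visit, up to 3 years.

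No section fixes the date of database lock or says how the 1-year objective and the all-follow-up analysis fit together.

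**The concern.** The objective, the sample size and the blinded check all concern the first year. The sentence that defines the primary analysis does not. Because a 365-day-censored analysis is listed separately, the primary one must be meant to include later events.

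Four consequences follow.

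- The protocol contains two candidate primary results, one for the 1-year objective and one for the analysis section, and they can disagree.
- The stated 80% power belongs only to the 1-year comparison.
- With staggered entry, the effect estimated by the all-follow-up test depends on accrual speed and on when the database is closed, because these decide how much follow-up beyond year 1 enters.
- The key secondary endpoint is gated on the primary result, so the ambiguity carries into the type I error procedure.

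**Working it through.** **Step 1. Reproduce the plan's sample size.**

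Inputs from sections 10 and 10.1: control rate 0.15; 30% reduction, so 0.15 × 0.70 = 0.105; power 80%; one-sided 5%. Allocation of 1:1 is assumed, as the ratio is not stated. The mean rate is 0.1275.

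n per arm = [1.645·√(2·0.1275·0.8725) + 0.842·√(0.15·0.85 + 0.105·0.895)]² / 0.045²
= (0.776 + 0.396)² / 0.002025 ≈ 678.2, rounded up to 679.

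Total 2 × 679 = **1358**, an exact match. The plan is therefore powered for a difference in 1-year risk.

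**Step 2. The 1-year analysis as a log-rank test.**

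- Expected events: 679 × (0.15 + 0.105) ≈ 173.
- Hazard ratio (HR) implied by the two rates: ln(0.895)/ln(0.85) = 0.683, so |ln HR| = 0.382.
- Schoenfeld power: Φ(½·√173.1·0.382 − 1.645) = Φ(0.87) ≈ 81%, in line with the planned 80%.

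**Step 3. What happens when later events count (formula).**

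The protocol gives neither a control rate nor an effect beyond year 1, so both are assumptions here. The control hazard is held at −ln(0.85) = 0.1625 per year, the year-1 HR is 0.683 and the later HR varies. The log HR is averaged over events. Every patient is followed for the same time.

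| HR after year 1 | 2 years: events | 2 years: power | 3 years: events | 3 years: power |
|---|---|---|---|---|
| 0.683 (sustained) | 324 | 96% | 454 | 99% |
| 0.85 (weaker) | 338 | 81% | 480 | 84% |
| 1.0 (none) | 351 | 55% | 502 | 43% |

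Example, 2 years with no later effect: mean ln HR = (173.1/350.9) × (−0.382) = −0.188, so the average HR is 0.83. Power = Φ(½·√350.9·0.188 − 1.645) = Φ(0.12) ≈ 55%.

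**Step 4. Staggered entry (simulated log-rank tests).**

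Settings: 1358 patients, uniform accrual over 2 or 3 years (assumed), lock when the last patient reaches 1 year (assumed), constant control hazard (assumed), one-sided 5%. Both analyses were run on the same simulated data.

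- Events: about 173 within 1 year, against about 320 to 420 over all follow-up. With the planned year-1 effect, 46–59% of the events in the all-follow-up analysis lie outside the stated endpoint.
- Power over all follow-up: 96–98% if the effect is sustained; about 81–82% if the later HR is 0.85; about 55% (2-year accrual) or 49% (3-year accrual) if there is no effect after year 1. The 1-year analysis has about 80% in each case.
- Different verdicts from the two analyses: about 15–19% of trials if the effect is sustained or weakens, and about 30–38% if it stops after year 1. The figure reaches about 58% only in a late-effect pattern (HR 0.85, then 0.683), which departs from the plan's own year-1 assumption.
- Sensitivity: if the hazard after year 1 is half that of year 1, the share of events outside the endpoint falls to 31–44%, and power with no later effect is about 64% (2-year accrual) or 59% (3-year accrual).

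**The case against.** The strongest reply is that a time-to-event analysis of all follow-up is a legitimate design and often gains power. The protocol's background (section 3.5) cites an HR of 0.66 for myocardial infarction at 5 years, and a pooled HR of 0.72 for cardiac death or infarction at a median of 35 months. These come from other populations and endpoints, but they point towards lasting benefit. Under a sustained effect the written analysis beats the 1-year one, and much of the disagreement between the two is then the longer analysis finding a real effect that the shorter one misses. With a weaker later effect, power hardly changes. This part stands: the mismatch does not show that the trial is underpowered.

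A second reply is that the result is less open to choice than it looks. Adjudication is blinded and binding (section 9.9), the sample-size check is blinded (section 10.1), and no unblinded interim look is described. The lock date may also properly be left to the statistical analysis plan. This stands in part. The missing date alone would be no finding, but none of these safeguards settles which window is primary in an open-label trial.

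A third reply is that the lock may simply mean the 1-year lock. No section says so. Even then, patients enrolled early would contribute events beyond 365 days, and the separate 365-day analysis would have no purpose if the primary already stopped there.

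**Conclusion.** The concern holds. Sections 5.1 and 10.1 fix a 1-year question, and section 10 fixes a primary analysis that answers another one. This is a contradiction in the protocol's own text, not a detail deferred to a later plan. The figure of 1358 reproduces exactly as the 1-year sample size, so the 80% power does not carry over to the analysis named as primary.

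The size of the effect on power cannot be fixed from the document. It ranges from a gain (96–98%) through no change (about 81%) to a marked loss (about 55% or 49%). These figures rest on assumed accrual of 2 to 3 years, lock at the last patient's 1-year point, a constant control hazard and assumed later hazard ratios. The conclusion that roughly a third to over half of the analysed events would fall outside the stated endpoint holds under both later-hazard assumptions tried.

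**What to change.** Replace the sentence in section 10 with: *The primary analysis is the comparison of time to first POCE event, with follow-up censored at 365 days after randomization, performed when the last patient has completed 1 year.* Make the all-follow-up analysis supportive, or place it under the 3- and 5-year secondary objectives.

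The cost is one sentence. The 365-day analysis is already planned, 1358 (before attrition) still gives 80% power at the protocol's one-sided 5% level, and no patients, visits or data are added.

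If the sponsor prefers all follow-up as primary, that also resolves the conflict. Section 5.1 would then have to be restated to match, the lock defined in advance, and section 10.1 recalculated with explicit assumptions about the event rate and effect after year 1.

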10.1 Determination of sample size

Data regarding death, MI, stroke and revascularization at 1 year in patients ≥ 75 years with MI and multivessel disease treated with culprit only revascularization are lacking. Taking into account available data (see tables below) and our preliminary data coming from “The frailty in elderly patients receiving cardiac interventional procedures (FRASER) program”, we estimated a conservative 15% rate of the primary endpoint at 1 year in the culprit-only strategy group. Considering that functional assessment should reduce the primary endpoint of at least 30% (see table below), 1358 patients are required to have a 80% chance of detecting, as significant at the 5% level, a 30% difference in the primary outcome between the two groups considering a 15% rate of the primary endpoint in the control group. Considering a 2% attrition rate final sample size is inflated to 1385 patients. After at least 900 patients have completed the 30-day follow-up, the assumption of the sample size calculation will be checked by estimating the Kaplan-Meier 1-year risk of having reached the primary endpoint. Unadjudicated data will be used for this purpose. No randomization information will be available and all the evaluation on the sample size will be performed in a blinded fashion. If the pooled event rate will be considerably lower than expected the sample size may be increased.

Ischemic outcome at 1 year in patients with ACS treated with culprit-only revascularization

Study	MI	Repeat revascularization	MACE
Compare acute	4.7%	17.5%	20.5%
Culprit	2.7%	8.2%	21.2%
Prami	8.6%	19.9%	22.9%
Danami-3-Primulti	5%	9%	22%
Translate-ACS	7%	17%	22%

Primary endpoint reduction with functional guided revascularization in ACS setting

Study	Primary endpoint	HR
Compare acute	MACCE*	0.35 [0.22-0.55]
Danami-3-Primulti	all-cause mortality, reinfarction, or ischaemia-driven revascularisation	0.56 [0.38-0.83]

*all-cause mortality, nonfatal myocardial infarction, any revascularization, and cerebrovascular events.

11 SUB-STUDIES

Sub-studies may be added at a later date based on the recommendation of the Steering Committee. The analysis and reporting of these sub-studies will be totally separate from the main study.

12 DATA MANAGEMENT

Data will be collected on electronic case report forms (eCRFs). The CRF must be signed by the investigator or other appropriate individuals who are authorized by the investigator. Signing of the ‘Study completion – Investigator’s statement CRF’ must be done by the investigator and is considered to be the final authorization of the CRFs.

13 ANGIOGRAPHIC AND FUNCTIONAL CORE LAB

The central core lab will review all the angiographies from the enrolling centers and will review the evaluation of the culprit lesion and the % diameter stenosis and the functional evaluation of all the stenosis with evaluation of the functional pitfalls. If centers will not properly evaluate culprit lesion or if relevant pitfalls in the functional evaluation will be present in more than 3 cases in the same center, the center will receive a proper retraining on functional evaluation. If the center even after the functional retraining will not be able to perform a proper functional evaluation, the enrollment will be stopped.

14 ETHICAL AND REGULATORY STANDARDS

14.1 Good Clinical Practice

The procedures set out in this protocol are designed to ensure that the investigator abide by the principles of the Declaration of Helsinki and Good Clinical Practice Guidelines (ICH-GCP) in the latest version, in conduct, evaluation and documentation of the study. A copy of these documents will be provided to each centre. The study will be carried out in keeping with local legal requirements and International regulations.

14.2 Informed Consent of the Patient

Patients who meet all inclusion criteria and none of the exclusion criteria are deemed eligible. Before being enrolled into the clinical study, the patient must provide written consent to participate in the study after the nature, scope and possible consequences of the clinical study have been explained both orally and in writing. Patients should be aware that they will be followed for the study whether or not they undergo invasive strategy as allocated. All patients who signed informed consent must be listed on the Screening Log.

14.3 Approval of the Study Protocol

Before the start of the study, the study protocol and the informed consent form used at the site and other appropriate documents must be submitted to and approved by the local Ethics Committee or Institutional Review Board and the appropriate regulatory authorities in accordance with local legal requirements. Documentation of Ethics Committee/IRB approvals will be required before sites are activated to randomize.

14.4 Maintenance of Records

The Investigator agrees to obtain a correctly completed informed consent form for each patient included in the study. The investigator will maintain a personal list of patient numbers and patient names to enable records to be found at a later date. The Investigator must maintain all study records, patient files and other source data for the maximum period of time permitted by the hospital, institution or private practice. However national regulations should be taken into account, the longest time having to be considered. For

trials performed in the European Community, the Investigator is required to arrange for the retention of the patient identification codes for at least 15 years after the completion or discontinuation of the trial.

14.5 Confidentiality

All patient names will be kept confidential. Patients will be identified throughout documentation and evaluation by the number allotted to them by the study. The patients will be assured that all findings will be stored on computer and handled in the strictest confidence. The Investigator agrees to maintain the confidentiality of the study protocol.

15 ADMINISTRATIVE RULES

15.1 Curriculum vitae

An updated copy of the curriculum vitae for each Investigator and co-Investigator will be provided prior to the beginning of the study.

15.3 Record retention in investigating centre(s)

The Investigator must maintain all study records, patient files and other source data for the maximum period of time permitted by the hospital, institution or private practice. National regulations, however, should be taken into account, the longest time having to be considered. For trials performed in the European Community, the Investigator is required to arrange for the retention of the patient identification codes for at least 15 years after the completion or discontinuation of the trial.

16 OWNERSHIP OF DATA AND USE OF THE STUDY RESULTS

The Study Principal Investigator and the Study Chair have ownership of all data and results collected during this study. Full publication rights of the study data solely reside with the Study Principal Investigator and the Study Chair.

17 PUBLICATIONS

All study presentations and/or publication of the results will be based on clean, checked and validated data in order to ensure the accuracy of the results. Publication of the main findings of this study will be authored based on the contributions of the individuals to the overall study. All the trial participants (Investigators and committee members) make a prior delegation of responsibility for primary presentation and/or primary publication of the results to the Study Principal Investigator and the Study Chair.

18.2 INSURANCE

Subjects who participate in this study will be insured against study related injury according to local regulatory requirements. A copy of the certificate is filed in each investigator site file and in the trial master file.

18.3 FUNDING AND SUPPORT

This study is an Investigator Initiated Trial supported by an unrestricted grant from different public and private companies (for details see attachment – appendix A). Study supporters have no role in the study design, conduct, and publication of the primary as well as any secondary manuscripts.

